## Evaluating the Impact of an Emotion Regulation Intervention on Emotion Perception

### Purpose of the Study

**Aim 1:** To evaluate the short-term impacts of an emotion regulation intervention on emotion perception in the laboratory. In the laboratory training session, we will compare performance on behavioral emotion perception tasks between participants who receive the intervention, a training in an emotion regulation skill (i.e. mindful breathing), and participants in the control conditions (perspective-taking and worry inductions). **Hypothesis 1:** We predict that participants in the emotion regulation intervention condition will show less negative bias in their performance compared to participants in the control conditions. We also predict that intensity of emotional distress will be associated with negative biases.

**Aim 2:** To investigate the longitudinal effects of this intervention on emotion perception outside the lab using experience sampling. After the laboratory training session in aim 1, participants in both groups will receive an auditory reminder of the emotion regulation skill (a specific tone) three times a day through their mobile phones for one week and then will complete emotion perception tasks. Using our method of generalization, the participants in the intervention group have learned to associate the tones with reductions in emotional distress. For this aim, we will compare changes in performance on the emotion perception tasks over time between the three groups. **Hypothesis 2:** We predict that these cues will lead to greater decreases in negative biases in emotion perception over time compared to the control conditions. We will also test whether changes in emotional distress and regulation mediate the longitudinal changes in emotion perception performance.

### Background & Significance

Emotion perception problems are a transdiagnostic problem in mental health. Dysfunctional social processes, such as problems with perceiving and understanding other people's emotional expressions, are some of the main targets of mental health treatment emphasized within the Research Domain Criteria (RDoC) of the National Institute of Mental Health. Recent efforts in the NIMH have included assessing and targeting deficits emotion perception, one of the core social cognition processes that are impaired in schizophrenia. (Pinkham et al., 2014) However, emerging evidence has revealed that problems with emotion perception are also associated with many affective and personality disorders that are characterized by emotion dysregulation, such as depression, anxiety disorders and borderline personality disorder (Daros, Zakzanis, & Ruocco, 2013; Lazarus, Cheavens, Festa, & Zachary Rosenthal, 2014; Plana, Lavoie, Battaglia, & Achim, 2014; Schreiter, Pijnenborg, & aan het Rot, 2013). These problems often manifest as negative biases in emotion perception, the tendency to judge other people's emotional expressions negatively (Bradley, Mogg, White, Groom, & Bono, 1999; Dyck et al., 2009; Joormann & Gotlib, 2006) that contribute to further emotional difficulties (Rapee & Heimberg, 1997) and serious psychosocial problems such as violent offending, (Jolliffe & Farrington, 2004) aggression (Dodge, 1993), poor relationship quality (Carton, Kessler, & Pape, 1999) and general psychiatric distress (Crick & Dodge, 1994). Negative biases in emotion perception may also be a vulnerability factor for psychopathology, as there is evidence that problems with perceiving emotions in facial expressions are associated persistence and relapse of depression (Bouhuys, Geerts, & Gordijn, 1999). Therefore, there is a need for effective interventions for problems with emotion perception across affective and personality disorders. As these disorders are often comorbid (Grant et al., 2004),

effective interventions should target and treat transdiagnostic processes associated with social dysfunction in these disorders.

Novel, targeted, and transdiagnostic interventions are needed for problems emotion perception in affective and personality disorders. There is recent interest in clinical psychology to move away from labor and time-intensive treatment packages and to develop brief, accessible interventions (or “micro-interventions”) that target transdiagnostic processes underlying dysfunction across different psychiatric disorders. Because mental health providers often find that personality disorders and related interpersonal issues often do not respond to traditional psychotherapies (Beck, Davis, & Freeman, 2015), new approaches to interventions for social deficits are especially needed. An emerging, promising approach to improving social functioning is targeting psychology processes involved in social interaction (i.e. social cognition). (Penn, Sanna, & Roberts, 2008) Preliminary intervention efforts have demonstrated that remediation of problems perceiving emotional expressions are effective within schizophrenia (Kurtz & Richardson, 2012), and autism spectrum disorders (Roelofs et al., 2016). However, these interventions treat problems that are specific to these disorders (e.g. lack of knowledge of social cues) and do not target and treat the problems associated with affective and personality disorders (e.g. negative biases). In absence of effective emotion perception treatments for these populations, more research is needed to identify and target psychological processes that interfere with social processes within affective and personality disorders. To address this gap in the literature, I propose targeting specific psychological states that regularly interfere with emotion perception within these disorders.

Difficulties regulating emotional distress may lead to negative biases in emotion perception. Difficulty reducing intense, negative emotions is a potential target for treating negative biases in emotion perception. First, emotion perception deficits may be a serious issue within patients with affective and personality disorders characterized by emotion dysregulation, problems managing and reducing negative emotional experiences (Gross & Muñoz, 1995). Beyond the diagnoses, problems managing one’s own negative emotional states interferes with many social cognitive processes, including perceiving and understanding other people’s emotional expressions (Decety & Lamm, 2006; Eisenberg, Fabes, Guthrie, & Reiser, 2000). Specifically, research in healthy samples has demonstrated that increases in negative emotions lead to negative biases in emotion perception tasks (Chepenik, Cornew, & Farah, 2007; Niedenthal, Halberstadt, & Margolin, 2000; Schmid & Schmid Mast, 2010). These findings can be interpreted as a mood-congruence effect, in which a person’s emotional state leads them to selectively attend to and encode stimuli in the environment that is consistent with that emotion (Forgas & Bower, 1987). Furthermore, some researchers have argued that this effect may be particularly common within individuals who have chronic emotion dysregulation (i.e. borderline personality disorder (Daros et al., 2013; Domes, Schulze, & Herpertz, 2009)), whose social behavior is particularly mood-dependent. In line with this argument, our previous research demonstrated that high activation of negative emotions decreases sensitivity to other people’s emotional expressions across anxiety disorders, depressive disorders, and personality disorders (McMahon, Kim, Fang, Neacsiu, & Rosenthal, in press). Therefore, states of unregulated, intense negative emotions (i.e. distress) may often impair emotion perception abilities within people diagnosed with clinically significant emotional difficulties. We hypothesize that training patients to regulate their distress with emotion regulation skills will lead to less negative biases in emotion perception compared to patients who do not receive this training.

Mindfulness is a promising emotional regulation skill that could reduce negative biases in emotion perception. Identifying a brief intervention that effectively reduces negative emotions is necessary to investigate the impact of emotion regulation on emotion perception. Previous research has shown that mindfulness is a skill that is positively associated with both emotion perception ability and emotion regulation (Quaglia, Goodman, & Brown, 2015). First, mindfulness can be used to modulate experiences of negative emotions (Chambers, Gullone, & Allen, 2009; Roemer, Williston, & Rollins, 2015). For example, one study found that a 15-minute mindful breathing induction led to less negative emotional responses to negatively-valenced stimuli than control condition (a worry induction) (Arch & Craske, 2006a). Secondly, brief mindful breathing interventions can also lead to improvements in emotion perception. (Tan, Lo, & Macrae, 2014) Taken together, findings suggest that mindful breathing can be used as an emotion regulation skill that may have beneficial impacts on emotion perception. To our knowledge, these relationships have yet to be tested within clinical samples with emotion dysregulation. Given its established effect on emotion regulation, a mindful breathing skill will be taught to participants as an emotion regulation skill as a micro-intervention. A useful comparison condition would be a micro-intervention that targets perspective-taking (Jackson, Meltzoff, & Decety, 2005), another social cognitive process related to perceiving other people's emotions. Perspective-taking inductions may share similar mechanisms as mindfulness as another type of metacognitive intervention, but they do not address dysregulated emotions. Therefore, a perspective-taking micro-intervention will be used in this study as the active comparison condition.

Our team's intervention that generalizes emotion regulation skills is a novel approach to testing if reducing emotional distress reduces emotion perception biases. To study the longitudinal effects of emotion regulation skills on emotion perception, these skills must be applied over time in patients' daily lives. In almost all behavioral therapies, the learning process occurs inside a clinic setting, and patients are expected to transfer this learning outside the clinic setting to the natural environment. However, patients often find it extremely difficult to generalize newly learned adaptive responses from one context to another (Stokes & Osnes, 2016). A key principle that can be used to facilitate generalization of newly learned behavior across contexts is: stimuli that are paired with training and transported into relevant contexts in the natural environment can be used as functional mediators to promote generalization. (Stokes & Osnes, 2016) This has been tested in our lab within adults with a variety of psychiatric diagnoses all characterized by having high difficulties with emotion regulation. Preliminary findings from our NIMH-funded study with emotionally dysregulated adults, "Evaluating a Novel Method of Generalizing Emotion Regulation" (IRB #: Pro000035922), demonstrated that within the lab, auditory reminders of habituation (i.e. natural reductions in emotional arousal over time) reduced emotional distress ( $F=6.75$ ,  $p=.011$ ) and arousal ( $F=7.05$ ,  $p=.009$ ) significantly more than a control condition. Emotional distress and arousal were assessed with both self-report (e.g. Subjective Units of Distress) and physiological measures (e.g. galvanic skin conductance). Reminders delivered via mobile phones over one week also significantly reduced emotional distress compared to placebo sounds ( $X^2=11.54$ ,  $p<.001$ ). These findings suggest promise for the use of novel reminders of learned emotion regulation skills to improve the ability to perceive other people's emotions in real social contexts. The next steps in this research program is to test the effects of this intervention on other psychological processes that are fundamental to daily functioning, such as emotion perception.

In sum, this study investigates the impact of a novel, generalizable emotion regulation micro-intervention on emotion perception biases in a transdiagnostic sample of adults. Negative biases in

emotion perception are present within a wide range of psychiatric populations characterized by emotional difficulties and may contribute to debilitating social dysfunction. These deficits call for brief, accessible and effective interventions that target transdiagnostic processes that lead to these emotion perception biases. Therefore, this study proposes to investigate if a brief, emotion regulation intervention reduces negative biases in emotion perception within a transdiagnostic clinical sample with emotion dysregulation. This study will leverage our lab's translational method of generalizing learned emotion regulation skills to real social contexts through mobile-phone technology. We will compare the effects of this emotion regulation intervention with two comparison conditions that involve inductions that have been shown to increase emotional distress in response to stressful experiences: a worry induction and a perspective-taking induction. The findings from this study will determine whether problems with emotion perception can be reduced by helping patients manage their own emotional experiences in adaptive ways. These findings will inform larger clinical trials in larger samples and over longer periods of time. Therefore, this proposed project could pave the way for a new approach to treating emotion perception and other social processes in a wide range of clinical populations.

## Design & Procedures

This study is funded by Duke University Bass Connections Project Teams, through Duke Institute for Brain Sciences (DIBS). It is also funded by the Varela Award from the Mind & Life Institute.

**Study Overview:** This study will be a three-group study and will broadly follow the protocols of our team's previous study, "Evaluating a Novel Method of Generalizing Emotion Regulation" (Pro000035922). The study will be conducted over two sessions in the lab (intake and training sessions), followed by one week of receiving mobile phone prompts (testing phase). In the first intake session, all participants will be assessed for psychiatric diagnoses and complete the emotion perception tasks. Then, the participants will return one week later for the training session. Participants will be randomized to one of three groups: 1. Mindful Breathing, 2. Habituation, or 3. Control condition. After the training session, all participants will receive mobile phone prompts during the one-week testing phase. At the end of testing phase, all participants will complete the self-report measures of psychological functioning and the emotion perception tasks through an online survey. Emotional distress will be measured repeatedly throughout the study. See figure for a summary of the main procedures in the study protocol, with measures that may be used in primary and exploratory analyses:

**Recruitment and Assessment.** Before being recruited into the study, potential participants will complete a phone screen—a pre-experiment screening questionnaire (see Phone Screen document) or complete an online survey done through Qualtrics to assess certain exclusion and inclusion criteria (see inclusion/exclusion criteria in section 5). As the phone screen collects PHI (e.g. name, email and/or telephone number, knowledge of psychological symptoms, etc) in order to determine eligibility for the study, we request the waiver of consent to collect this information prior to informed consent. Potentially eligible participants will come to the lab for their intake session to fully determine eligibility for the study (see Request for Waiver of Consent). Upon arrival, a Clinical Assessor ([name] or [name]) will review the consent form, answer any questions, and obtain written informed consent. The Clinical Assessor then will administer diagnostic interviews (i.e. Structured Clinical Interview for

DSM-5 (SCID-5)(First, Williams, Karg, & Spitzer, 2015)) and self-report instruments needed to assess all other inclusion/exclusion criteria (see section 5).

## Measures and Tasks

Interviews: During the intake session, diagnostic exclusions and current/past prevalence of Axis I and II diagnoses will be determined by the Structured Clinical Interview for Mental Disorders-I and II (SCID-I and II for DSM-5), interviews with demonstrated reliability used in our lab. The Treatment History Interview, brief version (B-THI; Linehan & Heard, 1987) will also be used at the intake session to assess previous and ongoing psychiatric services received and the NART will assess reading ability. All interviews will be videotaped or audio recorded and [name] will determine the reliability of every tenth interview. These video and/or audio recordings will be recorded directly onto the assessor's Duke computer, using a USB connected web camera that is connected to the hard drive of that computer. The recordings do contain PHI and thus the Duke lab computer used for recording has been encrypted with PGP. These video/audio files will be only temporarily stored on the local Duke computer and will be moved to Department of Psychiatry & Behavioral Sciences protected folder.

If the participant recently took part in another study at CBRTTP, he or she may not be required to complete all portions of the SCID interviews. Specifically, if the participant completed a SCID-I diagnostic interview with one of our study assessors within the previous four weeks, he or she would only be required to complete any portions of the SCID-I not completed as part of the earlier study assessment. If the participant completed the SCID-II within the previous six months, he or she would not be required to complete the SCID-II. In those cases, data from the earlier assessments would be used for this study. These procedures reduce the burden on the participant by eliminating the need to duplicate lengthy interviews, while still ensuring that the data is current.

Emotion Perception: The main outcome measure of emotion perception will be assessed with behavioral tasks, described below.

(1) Emotion Perception Bias Task (EPBT). This behavioral assessment is adapted from other studies investigating the effects of mood on emotion perception biases (Dyck et al., 2008; Schmid & Mast, 2010). In this task, participants will view photographs of people's faces expressing either a negative emotion (e.g. angry), positive emotion (e.g. happy). These photos will be displayed to participants one at a time for a brief period, and then asked to judge the emotion in a multiple-choice format (e.g. "happy" or "angry"). At the end of this task, participants are asked to rate how confident they were in the accuracy of their responses on a 0-100 scale.

(3) The Bell Lysaker Emotion Recognition Task (BLERT) (Bell, Bryson & Lysaker, 1997) measures the ability to identify affect cues. It is an audio-visual task designed to elicit a person's ability to discriminate seven emotional states (i.e. happiness, sadness, fear, disgust, surprise, anger or no emotion) given facial, voice-tonal and upper-body movement cues. The BLERT consists of twenty-one, 10-second vignettes (using the same male actor) containing one of three monologues involving a work related topic. After each vignette, the tape is paused and the participant circles the corresponding emotional label on an answer sheet. After identifying the emotion for each video, participants are asked to rate how confident

they were in the accuracy of their response on a 0-100 scale. Performance is indexed as the total number of correctly identified emotions (ranging from 0 to 21). Test scores include the total number of correct responses, the number of correct positive affect responses (happy and surprise), the number of correct negative affect responses (sadness and fear), the number of correct difficult responses and number of correct easy responses.

(3) A phone-based assessment of emotion perception, adapted from procedures used in text-based emotion perception research in healthy populations (Cheshin, Rafaeli, & Bos, 2011). Participants receive standardized text messages that are previously rated for emotional valence on a 0 (very negative) to 9 (very positive) scale by independent raters. To increase ecological validity, participants are told that these messages have been sent by the experimenter, who is expressing an emotion through the message (e.g. "I just got into an argument with a friend, so I'm not having a good day"). After participants receive the text message, they are instructed to rate the valence of the emotion of the message on the same 10-point scale. This phone-based emotion perception task will only be administered during the one-week testing phase. See the text message script document for the text message content participants would receive during testing phase.

Emotion: Emotional arousal will be measured through self-report and physiological measures: (1) Skin conductance will be measured using Ag-AgCl electrodes, which are connected to a Biopac MP150 device in an adjacent room. Amplified signals of analog data are converted to digital form and filtered using Biopac's Acqknowledge Software and are stored in a database on the computer. (2) Subjective units of general psychological distress (SUDS; visual analogue scale from 0-100); (3) the Sedation Scale (SS), a self-report measure of emotional and general levels of arousal, and (4) the PANAS-2 (Watson, Clark, & Tellegen, 1988), a measure of current emotional state.

Face-reader data collection. We have acquired new software (Facereader from Noldus) that can be used to analyze facial expressions from an inputted video and to output emotional experiences resultant from the facial analysis. This software complements the physiological data acquisition that we are doing and can add a new dimension to our data collection and analysis. We plan to video record participant's faces during the stressor and regulation periods of the study using a Microsoft webcam that is connected directly to a Duke approved laptop or computer. We will ask at consent for special permission for this procedure. We will only record participants' faces if consent is given. These recordings will be transferred right away at the end of the session on a secured server and deleted from the laptop (similar procedures as for assessment videos). The videos will be kept up to 6 years post study finish and deleted within that timeframe.

Psychological Functioning: Exploratory outcome variables will be changes in self-reported impairments in daily functioning and other psychiatric symptoms. These include:

1. Difficulties in Emotion Regulation Scale (DERS) (Gratz, 2004)
2. Interpersonal Reactivity Index (IRI),(Davis, 1980)
3. Toronto Mindfulness Scale (TMS) (Lau, et al., 2006),

4. Basic Empathy Scale (BES) (Carre et al., 2013)
5. Patient Health Questionnaire-depression module (PHQ-9) (Kroenke & Spitzer, 2002)
6. Social Interaction Anxiety Scale (SIAS; Mattick & Clarke, 1998)
7. NIH Toolbox Adult Social Relationship Scales (NIH SRS) (Cyranski, 2013)
8. Ambiguous Intentions Hostility Questionnaire (AIHQ-A; Combs et al, 2007)
9. Early Memories Task (EMT; Mayman, 1968)
10. Psychological Flexibility Questionnaire (PFQ; Ben-Itzhak, 2014))

Personally-Relevant Emotional Stressor Task. Using the method used in our previous studies, we will create four negative emotional arousal scripts that will be used in a random order during the first lab session. The clinical assessor will ask the participant to describe three of the most recent stressful experiences in their lives within the past two weeks (a timeline that has shown to be feasible within our previous studies with emotionally dysregulated participants). Participants will write a description of each event, and the clinical assessor will work with the participant to establish a clear story for each event that can be recited in approximately 30 seconds. The clinical assessor will digitally record these scripts into .mp3 files, which will be used in random order as the emotional stressors. Each stressor is presented to the participant three times. Participants will be instructed to listen carefully to the recorded stressor via headphones (30s) and to imagine the stressful experience as vividly as possible. All participants will be given these instructions, but additional instructions are given according to the experimental condition.

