#### Experimental Procedures

Intake Session: After determining eligibility, participants will complete measures of social and psychological functioning (DERS, IRI, PANAS-2, TMS, AIHQ-A, NIH SRS, PHQ-9, BES, EMT, SIAS, PFQ) and the two laboratory emotion perception tasks (BLERT, EPBT) through an online Qualtrics survey on a standard desktop computer in the laboratory. At this time, they will provide four recent stressful experiences for the personalized stressor task.

Training Session: All participants will come back to their lab for this session (ideally between 5-7 days after the intake session), which will take approximately 1.5 hours. First, all participants will be asked about: 1) current distress and suicidal urges (i.e. Suicide Risk Protocol), 2) any changes in medications since the previous visit, 3) nicotine, caffeine, and alcohol use that day, 4) subjective units of general psychological distress (SUDS; visual analogue scale from 1-9), 5) dissociation state, assessed using self-report (Dissociative-Tension States Scale 4 item version-DSS-4 from the DSS-acute), 6) levels of arousal with the Sedation Scale, and 7) current affect with the PANAS-2. Then, the experimenter will affix electrodes and will use Biopac MP150 hardware and AcKnowledge software for data acquisition. All participants will be assessed for baseline negative emotional arousal with psychophysiological (galvanic skin response) measures for five minutes. Then, participants will be randomized to one of three groups:

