Immediately after the emotional stressor task, all participants will again report: 1) subjective units of general psychological distress (SUDS; visual analogue scale from 0-9), 2) dissociation state, assessed using self-report (Dissociative-Tension States Scale 4 item version-DSS-4 from the DSS-acute), 3) levels of arousal with the Sedation Scale, and 4) current affect with the PANAS-2. They will then complete the laboratory emotion perception bias task and a manipulation check. Afterward, they will be oriented to the mobile phone prompts they will receive during the testing phase.

Testing Phase: During the one-week testing phase, participants in both conditions will receive three text-message prompts through their own phones randomly each day. These prompts will function both as an EMA measurement of self-reported negative emotional distress, as well as the delivery method of the tones. We will have a specific application, processed and stored on Heroku, that will receive and send text messages to participants via Twilio. In each prompt, participants will be asked to report on their current negative emotional distress (SUDS). When participants report high distress (i.e.,  $SUDS > 2$ ), they will automatically hear the tone by receiving a text message with an .mp3 file. The participants in the control conditions will also hear the tone despite having no previous associations with it, to control for potential placebo effects. After hearing this sound, participants will report again on

their distress, then complete the phone-based emotion perception task. As a manipulation check, the participants in the emotion regulation intervention condition will be asked if they actually used the mindful breathing skill. If the participant does not meet criterion for high distress, they will instead receive a text response on their phone thanking them for their response (see text message sample script document).

All participants will complete the laboratory emotion perception tasks and self-report measures of emotion and psychological functioning through an online Qualtrics survey at the end of this testing phase. They will also complete an exit questionnaire through this Qualtrics survey (see exit questionnaire document).

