Specific Aim 1: Aim 1 will determine if the emotion regulation intervention leads to fewer negative biases in emotion perception during the laboratory training session. For this aim, we will conduct ANCOVA analyses to study group differences in performance on the emotion perception laboratory tasks, controlling for their baseline scores assessed in the intake session. To compare the conditions' impacts on negative biases, we will analyze group differences in 1) number of trials with neutral facial expressions are misclassified as negative emotions; 2) accuracy for positive emotions and negative emotional expressions. We will also examine the relationship between emotional distress and emotion perception. Hypothesis 1: Participants in our emotion regulation condition will have less negative bias in emotion perception (e.g. fewer neutral faces misclassified as negative, lower accuracy for negative emotions, higher accuracy for positive emotions) compared to participants in both the control conditions. Even though the perspective-taking and mindful breathing conditions may have similar effects (e.g. increasing attention to social cues (Olsson et al., 2016; Quaglia, Goodman, & Brown, 2016)), perspective-taking inductions may still lead to mood-congruent biases by increasing negative emotional responses (Lamm, Batson, & Decety, 2007). Therefore, we predict that the emotion regulation intervention would reduce this bias significantly more than both the worry and perspective-taking conditions. We also predict that intensity of emotional distress will be related to negative biases in emotion perception.

Specific Aim 2: Aim 2 will compare the changes in emotion perception over time between the emotion regulation breathing condition and the control conditions. For this aim, Multilevel modeling (MLM) will be used because it permits evaluation of longitudinal data on participants over time with trajectories for each participant examined as random effects. We will conduct MLM analyses to study group differences in changes in the laboratory emotion perception tasks assessed during intake (time 1), the training session (time 2) and after the testing phase (time 3). For the phone-based behavioral task, we will first examine the psychometric properties of this measure in this clinical sample. Then, we will analyze group

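### The phone emotion-perception task has no pre-training measurement, so it supports a group comparison of level and a within-week slope but not change from the pre-training level

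*Combined protocol and SAP*

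**What the plan says.** Measures and Tasks confines the phone task to one period: "This phone-based emotion perception task will only be administered during the one-week testing phase". Messages are rated from 0 to 9, and independent raters have scored each message on that scale beforehand.

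Experimental Procedures puts randomisation in the training session, before the testing week. Within a prompt, a participant reporting SUDS above 2 comes to the tone first: "they will automatically hear the tone by receiving a text message with an .mp3 file". The text continues "After hearing this sound, participants will report again on" "their distress, then complete the phone-based emotion perception task". At other prompts no phone task is described: "If the participant does not meet criterion for high distress, they will instead receive a text response on their phone thanking them for their response".

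Intake covers "the two laboratory emotion perception tasks (BLERT, EPBT) through an online Qualtrics survey", with no phone task.

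Purpose of the Study, Aim 2, promises a three-group comparison of change on the emotion tasks, without excepting the phone task, and states: "We predict that these cues will lead to greater decreases in negative biases in emotion perception over time compared to the control conditions". Data Analysis & Statistical Considerations, Specific Aim 2, gives the laboratory tasks a multilevel model over intake, training and the end of the testing phase. For the phone task it says "For the phone-based behavioral task, we will first examine the psychometric properties of this measure in this clinical sample", followed by group differences in valence ratings across the testing week. No baseline term is mentioned.

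**The concern.** A decrease needs a starting value. The first phone rating comes after the arms have been trained differently and after at least one tone, so it is not a pre-intervention value. A lower bias in the intervention arm during the week could reflect a fall in that arm or a rise in the comparison arms, and the phone data cannot tell these apart.

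This matters because the phone task is the only repeated measure of emotion perception in daily life. BLERT and EPBT measure recognition from faces, voice and video on up to three occasions. They do not measure how people read messages day to day.

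Stable differences between people in how they rate messages also stay in the error of the level comparison, with 24 completers per group planned.

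**Working it through.** **Which phone ratings exist**

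- Before training: 0.
- Before the tone within a prompt: 0, as the sequence is described.
- During the week: at most 3 per day × 7 days = 21 per person, and fewer whenever SUDS is 2 or below.

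**What level and slope each detect.** Take a group effect of size 1 and all 21 prompts answered.

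| Pattern of effect | Slope difference across the week | Difference in week mean |
|---|---|---|
| Fully present at the first rating | 0 | 1.0 |
| Growing linearly from 0 to 1 over the week | 1.0 | 0.5 |

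Hypothesis 1 predicts a group difference already in the training session. To the extent that this carries over to the phone task, the slope misses it.

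**The plan's own power figure.** Inputs from Data Analysis & Statistical Considerations: 72 participants (24 per group), alpha 5%, Cohen's f = 0.38, at least 80% power. With a one-way three-group F test and noncentrality N × f² = 72 × 0.38² = 10.4, power is 0.813, and 24 per group is the smallest size that reaches 80%. The figure reproduces. The smallest f detectable with 80% power at 72 is 0.374.

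**What a same-measure baseline would add.** Let r be the correlation between a person's baseline rating error and their testing-week mean. The documents do not give it, so the values below are assumptions. Adjustment multiplies the residual variance by 1 − r² and the standard error by √(1 − r²). The equivalent gain in sample size is 1/(1 − r²). Applying the plan's N and f to the phone task is an illustration only.

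| Assumed r | Variance factor | Standard error factor | Equivalent sample | Detectable f (from 0.374) | Power at f = 0.38 (from 0.813) |
|---|---|---|---|---|---|
| 0.3 | 0.91 | 0.954 (about 5% smaller) | 1.10 | 0.357 | 0.850 |
| 0.5 | 0.75 | 0.866 (about 13% smaller) | 1.33 | 0.324 | 0.914 |
| 0.7 | 0.51 | 0.714 (about 29% smaller) | 1.96 | 0.267 | 0.983 |

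The last row is optimistic. A few messages rated in one sitting would have to correlate 0.7 with ratings made in daily life, after a tone, at high-distress prompts.

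**The case against.** The case on the other side is strong in four respects.

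- **Change is not wholly out of reach.** Specific Aim 2 uses multilevel models with individual trajectories, so a group-by-time slope within the week can be estimated. Hypothesis 2 credits the cues, so change during the cue week is a fair reading of it. Change from intake would mix the training effect with the cue effect. This stands, but the slope still has no pre-intervention anchor.
- **Hypothesis 2 has a baseline-anchored test.** A reader might infer that it cannot be tested at all. The documents do not support that: BLERT and EPBT are taken at intake, training and after the testing phase, and the analysis section plans no change-from-baseline analysis for the phone task.
- **Randomisation protects the level comparison.** A reader might infer bias from the missing baseline. There is none from that source. Baseline means are equal in expectation, so the difference in level has the same expectation as the difference in change. What is lost is precision, a check on chance imbalance, and knowledge of which arm moved. The independent raters' valence also gives an external standard for scoring bias.
- **Rating style is only partly a problem.** A participant random intercept absorbs it in the slope contrast. It does not do so for the difference in level, where between-person variance still enters the standard error.

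**Conclusion.** The point holds as a limit on what the phone task can show and as a modest loss of precision. It supports a level comparison and a within-week slope, but not change from the pre-training level, although Aim 2 speaks generally of change on the emotion tasks. The cost is a standard error about 5% to 13% larger than it could be as a share of the unadjusted value, if r lies between 0.3 and 0.5. The true r is unknown. A claim that the baseline would be worth nearly double the sample needs r = 0.7, which nothing in the documents supports.

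This is worth correcting because the remedy is cheap and this is the only repeated field measure. It does not undermine the trial. A separate matter is that ratings arise only at prompts with SUDS above 2, a condition set after randomisation that the intervention may affect. A baseline would not cure that selection.

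**What to change.** 1. Amend the phone-task paragraph in Measures and Tasks so that a short set of pre-rated messages, not reused in the testing week, is rated before randomisation on the same 0–9 scale through the same text application.
2. In Specific Aim 2, use each person's mean deviation from the independent raters' valence on that set as a covariate in the phone-task group comparison.
3. State whether the phone estimand is level over the week or within-week slope. Do not describe it as change from baseline unless the set is added.
4. If the set is not added, adjust the phone comparison for the intake EPBT or BLERT score, naming in advance which one. These are already collected, though how well they predict message ratings is unknown.
5. Use the pre-randomisation ratings to supplement the psychometric check. They cannot replace it, since the check must also cover the repeated field ratings that are analysed.

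The cost is a wording change, a few minutes at intake and a few more pre-rated messages. The downsides are slight task familiarity, equal in all arms, and some possible weakening of the framing that the messages come from the experimenter.
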